3.1 General Design

This is a pilot study evaluating the feasibility of a novel modification to an established surgical procedure. The three operating surgeons are faculty members of the Division of Colon and Rectal Surgery in the Department of Surgery at DHMC. All radiographs will be reviewed by a single faculty of the Department of Radiology. We will use a modified Simon Two stage approach, the first phase will include five patients treated and followed sequentially. If there are 1 or fewer major wound occurrences (those requiring return to the operating room) then the study will proceed to the second phase which will include a total of 15 patients followed concurrently.

3.2 Primary Study Endpoints

The primary end point of the study is the validation of the mesh implantation procedure. We will assess the incidence of wound occurrences (defined as S-SSI, D-SSI, organ space SSI, dehiscence, and seroma formation) at 30days, with particular attention to wound occurrences requiring procedural intervention, including but not limited to, operative debridement, radiographically guided drain placement, or excision of the mesh. These incidences will be compared to historical controls.

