1.3.1 Safety Events

The previously referenced trial reported an overall 31% incidence of surgical site occurrences (SSO), which were defined as any surgical infection, wound dehiscence, wound breakdown, enterocutaneous fistula, seroma/hematoma formation, wound cellulitis, suture abscess, or nonhealing wound as described by the Ventral Hernia Working Group.⁴² The criteria for 30-day SSI was taken directly from the CDC criteria and was categorized into superficial, deep, and organ space infections. This included 7% wound dehiscence rate, 5% incidence of seroma or hematoma, 4% wound cellulitis rate, and a 1% enterocutaneous fistula rate. The SSI rate was (14%) where S-SSI was 8%, D-SSI was 3%, and O-SSI was 3%. In their cohort, only 4% of patients required mesh removal.²³ These findings are consistent with other reports of similar studies.^{26,27}

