1.4 Risk/Benefits

The primary concern is for surgical site occurrences. In the absence of mesh, the incidence of infection in ileostomy closures is estimated between 6 and 18%.⁴³⁻⁴⁵ This rate is minimized with the use of a purse string skin closure with iodine impregnated gauze packing vs partial closure with an open ended drain (Penrose type) or primary skin closure.⁴⁶ Prospective trial data estimates the overall incidence of infections when bioabsorbable mesh is placed in Class II and III ventral hernia repairs at 18%. None required mesh explantation and all wounds eventually healed.²⁷ Other reports of macroporous polypropylene mesh in clean-contaminated and contaminated wounds suggest an infection rate of 7.1% for clean contaminated and 19% for contaminated cases.²³ Surgical site occurrences will be treated on an individual patient basis determined by the clinical consequences of the occurrence. Infection may potentially be treated with antibiotics, local wound care, operative debridement, radiographically guided drainage procedures, vacuum assisted wound closure devices, or mesh removal at the discretion of the study team. Other potential adverse events are those inherent to intestinal surgery; anastomotic leak, peritoneal abscess formation, bowel obstruction, or ileus, in addition to the risks associated with general anesthesia.

2 Study Objectives

Primary Objective: To validate the technical procedure of mesh implantation at the time of ileostomy closure and preliminarily determine the incidence of surgical site occurrences (particularly those requiring intervention) compared to standard ileostomy closure technique.

Secondary Objective #1: Measure and compare quality of life scores for aspects related to the procedure to those related to bowel function.

Secondary Objective #2: To evaluate the process for longitudinally monitoring for the occurrence of hernia at site of stoma closure. We will evaluate our study protocol for the feasibility of performing a larger trial by measuring recruitment, retention of patients, adherence to the study protocol, and process assessment.

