6.3 Statistical Methods

The results of this study will be compared using a univariate analysis to historical control data obtained from the DHMC ACS-NSQIP database, with emphasis on surgical site occurrences including all types of SSI, and unplanned return to the operating room data points. The preliminary safety and feasibility data obtained from this study will be used to inform design of a larger study to test the hypothesis that the procedure can obtain a 50% reduction in the incidence of hernia formation at previous ileostomy sites compared to rates reported in the literature. The secondary objectives have not been previously reported in the literature either for patient reported outcomes or prospective evaluation of hernia formation. Further work, based on the data from this study, will attempt to show the superiority of the technique over currently used closure techniques as well as patient satisfaction with the procedure.

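### The primary wound endpoint in Section 3.2 counts fewer event types than the surgical site occurrences named in the objective (Section 2) and the analysis (Section 6.3)

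*Combined protocol and SAP*

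**What the plan says.** Besides validating the technique, the primary objective in Section 2 is to "preliminarily determine the incidence of surgical site occurrences (particularly those requiring intervention) compared to standard ileostomy closure technique". Section 6.3 plans a univariate comparison with historical controls from the institution's ACS-NSQIP data, "with emphasis on surgical site occurrences including all types of SSI, and unplanned return to the operating room data points". Neither section defines a surgical site occurrence.

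The only definition is in Section 1.3.1, which reports how an earlier trial of synthetic mesh in ventral hernia repair used the term: "defined as any surgical infection, wound dehiscence, wound breakdown, enterocutaneous fistula, seroma/hematoma formation, wound cellulitis, suture abscess, or nonhealing wound".

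Section 3.2 changes the term. The incidence to be assessed is that of "wound occurrences (defined as S-SSI, D-SSI, organ space SSI, dehiscence, and seroma formation) at 30days", with special attention to occurrences needing a procedure. The procedures are given as an open-ended list that names image-guided drainage as well as operative debridement and mesh excision. Section 3.2 then states: "These incidences will be compared to historical controls".

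**The concern.** The endpoint does not measure the objective as worded. The objective asks for the SSO rate, but the endpoint counts five event types. The open-ended phrase in Section 3.2 applies to the procedures, not to the events, so the event list reads as closed. Under it, a fistula, a haematoma or a wound that fails to heal counts only if it is also coded as an infection, dehiscence or seroma. Fistula matters most here, because Section 1.1 lists it among the historical arguments against mesh in contaminated or clean-contaminated fields.

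The control comparison has a similar problem. Section 3.2 would compare occurrences needing any procedure. Section 6.3 stresses SSO, including SSI, and unplanned return to the operating room. A patient who has radiologic drainage only is an event under the first and not under the reoperation item of the second.

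The pilot's safety data are meant to inform a randomised trial (Sections 2 and 6.3). A rate whose definition shifts between sections is a poor input to that design.

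**Working it through.** **Step 1. Compare the two lists.** The rates are those of the referenced trial, from Section 1.3.1.

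| Component | In 1.3.1 definition | In 3.2 list | Stated rate |
|---|---|---|---|
| SSI (superficial, deep, organ space) | yes | yes | 8 + 3 + 3 = 14% |
| Dehiscence | yes | yes | 7% |
| Seroma | yes | yes | 5% jointly with haematoma |
| Haematoma | yes | no | (within the 5%) |
| Wound cellulitis | yes | no | 4% |
| Enterocutaneous fistula | yes | no | 1% |
| Wound breakdown | yes | no | none given |
| Suture abscess | yes | no | none given |
| Non-healing wound | yes | no | none given |

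**Step 2. Reproduce the stated SSO rate.** 14 + 7 + 5 + 4 + 1 = 31%, which matches the overall figure in Section 1.3.1. The components therefore add up as though each patient was counted once. The last three rows contribute 0 points to the stated breakdown.

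**Step 3. Apply the 3.2 list to the same cohort.** The seroma/haematoma split is not given, so haematoma is assumed to lie anywhere between 0 and 5 points.

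- All of the 5% seroma: 14 + 7 + 5 = 26%, a shortfall of 5 points (5/31 = 16% relative).
- All of the 5% haematoma: 14 + 7 = 21%, a shortfall of 10 points (10/31 = 32% relative).

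**Step 4. Translate to 20 patients.**

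- Full definition: 20 × 0.31 = 6.2 expected events.
- 3.2 list: 20 × 0.21 = 4.2 to 20 × 0.26 = 5.2 expected events.
- Difference: 1 to 2 events.
- Chance that at least one of the 20 patients has an omitted event: 1 − 0.95^20 = 64% to 1 − 0.90^20 = 88%.
- Fistula alone: 20 × 0.01 = 0.2 expected events.

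**Step 5. Set this against sampling error.** Exact 95% intervals are 5.7% to 43.7% for 4/20, 8.7% to 49.1% for 5/20 and 11.9% to 54.3% for 6/20. The definitional gap is much smaller than the width of any of these.

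**Step 6. Compare the outcomes for the control comparison.** Section 3.2 names the five-item wound occurrences, with those needing any procedure as the focus. Section 6.3 names SSO, including SSI, and unplanned return to the operating room. No section reconciles the two or lists which events the registry extract contains.

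**The case against.** The strongest reply is that Section 3.2 is the protocol's own operational definition. Section 1.3.1 only reports how another trial defined SSO, and nothing says this protocol adopts that wording. A narrower list fixed in advance is a legitimate choice. This stands in part: the rate is too low only relative to the broader definition. It does not explain why Sections 2 and 6.3 use the broader term with no other definition on offer.

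The omitted events are also not lost. Section 7.2 requires all adverse events to be sought by questioning and recorded. That is correct, but they would sit outside the primary rate. Most of the certain 5-point loss is cellulitis, which is not specific to mesh and may partly be coded as superficial SSI, so the true gap could be smaller.

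Three stronger readings are tempting, and the documents do not support them.

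- A reader might infer that the pilot's rate will look favourable against a 31% benchmark. The 31% is background from ventral hernia repair. No threshold is set against it, and Section 1.3 calls infection and hernia recurrence outcomes acceptable, not the SSO rate.
- A reader might infer that the endpoint cannot match the control data. The registry variables are not listed, and Section 6.3 states an emphasis, not a closed list. If the controls were scored on the 3.2 list, the comparison would be like for like.
- A reader might infer that the five-item list also governs the wound-occurrence rules in Sections 3.1 and 7.4. Those sections use the same term but do not refer to Section 3.2, so this is an open ambiguity and not an established effect.

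**Conclusion.** The point holds as an inconsistency between objective, endpoint and analysis. The primary rate in Section 3.2 omits six components of the only SSO definition in the document, including fistula, and Sections 3.2 and 6.3 do not name the same outcomes for the control comparison.

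The size is modest. It rests on three assumptions: that the ventral hernia rates indicate scale for ileostomy closure, that the listed components do not overlap, and that haematoma accounts for between none and all of the joint 5%. On those, the 3.2 list gives a rate 5 to 10 points lower, with the upper end an extreme. At n = 20 no analysis could separate that from chance, but the shift is systematic and would carry into the planning of the next trial. This is a change that should be made. It does not show that the pilot's conclusions would be wrong.

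**What to change.** - Use one SSO definition in Sections 2, 3.2 and 6.3. Add enterocutaneous fistula, haematoma, wound cellulitis, wound breakdown, suture abscess and non-healing wound to the present list.
- Give 30-day criteria for wound breakdown and non-healing wound. The skin is closed by purse string over a packed cavity (Section 5.2), so these two items cannot be scored consistently without them.
- Report SSO requiring procedural intervention as the key subset.
- State which components the registry records. Compare with controls only those counted the same way in both sources, for example SSI by type and unplanned return to the operating room, if the extract confirms them.
- Report the full SSO rate and the radiologic-drainage rate descriptively, for the study cohort only.
- State whether the wound-occurrence wording in Sections 3.1 and 7.4 follows the same definition.

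The cost is protocol wording and a few case report form items, collected at visits already planned. The reported rate may be somewhat less favourable than under the present list.

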3.3 Secondary Study Endpoints

The secondary endpoints will be evaluation of the incidence of hernia formation at the ileostomy site on a prospective basis at 30 days and 6 month intervals thereafter until two years from the date of ileostomy closure. The Promis SF 2.0 8a Ability to Participate in Social Roles and Activities instrument will be used to assess quality of life and the Colorectal Functional Outcome (COREFO) instrument will be used to evaluate bowel function at each interval.

4 Subject Selection and Withdrawal

4.1 Inclusion Criteria

1. Age > 18years
2. Patient is undergoing closure of loop ileostomy
3. Patient has a diagnosis of left sided colon or rectal cancer treated with resection and diverting loop ileostomy
4. Patient has been evaluated by a qualified surgeon and found to be a suitable candidate for surgery

4.2 Exclusion Criteria

1. Pre-existing systemic infection at the time of ileostomy takedown
2. Cirrhosis, chronic renal failure requiring dialysis, or collagen disorder
3. On current immunosuppression (anti-TNF agents, chemotherapy, or prednisone >10mg/day)
4. Previous abdominal hernia repair with mesh placement
5. Concurrent procedures in addition to closure of diverting loop ileostomy
6. Ileostomy closure not completed through the previous stoma site (i.e. those requiring exploratory laparotomy for closure)

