By the completion of this pilot study, our expected outcomes are to have demonstrated a high level of procedural fidelity among the operating surgeons of the modified ostomy closure technique and comparable costs to the standard procedure as well as greater than 80% recruitment and retention of eligible participants, and greater than 90% adherence to the study protocol. We also expect to preliminarily demonstrate safety and similar quality of life compared to historical controls on short term follow-up. These results are expected to inform development of an appropriately powered, multiple center, randomized controlled trial comparing the effectiveness of our novel modification of ostomy closure technique to the standard technique.

3 Study Design

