4.4.2 Data Collection and Follow-up for Withdrawn Subjects

Data related to the time period of the subject's participation will be included in the analysis of the treatment effect. Should a subject be withdrawn from the study for any reason, survival data will be maintained in accordance with the guidelines for follow-up prescribed by the NCCN.

5 Study Procedures

5.1 Encounter 1

Patients will be assessed for ileostomy closure based upon completion of therapy after primary resection of their malignancy. Appropriate candidates will be determined at the operating surgeon's discretion based on customary evaluation of clinical status. The informed consent process will be initiated and the patient recruited into the study.

5.2 Encounter 2

This encounter is the operative procedure. The procedure for closing the ileostomy (i.e. bowel anastomosis) will be at the discretion of the surgeon, provided it is performed through the ileostomy site without additional laparotomy incisions. In accordance with SCIP guidelines, pre-operative intravenous antibiotic and subcutaneous pharmacologic venous thromboembolism prophylaxis will be administered. Patients with a history of MRSA infection will also receive a dose of intravenous vancomycin prior to the procedure.

The abdominal wall reconstruction portion of the procedure will be standardized to ensure consistency between surgeons. The posterior rectus sheath is closed with native tissue either primarily, using hernia sac if present, or bridged with Vicryl-type mesh and a quickly absorbing suture material. This is done to isolate the mesh from the peritoneal cavity. The retrorectus plane is developed using electrocautery and blunt dissection to provide adequate placement of mesh such that it overlaps the posterior sheath defect by a minimum of 3cm on all sides. The mesh is placed in this plane and secured in place with slowly absorbable monofilament (0-PDS preferred) sutures placed through the anterior fascia or with application of fibrin sealant at the surgeon's discretion. This space is then irrigated with

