6.4 Subject Population(s) for Analysis

The statistical analysis for this study will use an all-treated population: Any subject who participated in the study and underwent the study procedure. Patients without complete follow-up data will be excluded from the final analysis.

7 Safety and Adverse Device Effects

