All subjects for this study will be provided a consent form describing this study and providing sufficient information for subjects to make an informed decision about their participation in this study. See Attachment A for a copy of the Subject Informed Consent Form. This consent form will be submitted with the protocol for review and approval by the EC/IRB for the study. The formal consent of a subject, using the EC/IRB-approved consent form, must be obtained before that subject undergoes any study procedure. The consent form must be signed by the subject or legally acceptable surrogate, and the investigator-designated research professional obtaining the consent.

11 Study Finances

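### Exclusion 6 is an operative outcome known only after recruitment, and section 6.4 analyses only patients who underwent the procedure, so delivery of the mesh closure is assessed mainly where it could be carried out

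*Combined protocol and SAP*

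**What the plan says.** - **Exclusion 6 (section 4.2):** "Ileostomy closure not completed through the previous stoma site (i.e. those requiring exploratory laparotomy for closure". Exclusion 5 in the same list rules out concurrent procedures.
- **Recruitment (section 5.1, Encounter 1):** "The informed consent process will be initiated and the patient recruited into the study". The operation is Encounter 2 (section 5.2). The Ethical Considerations section adds that consent "must be obtained before that subject undergoes any study procedure".
- **Operation (section 5.2):** the method of bowel closure is left to the surgeon, "provided it is performed through the ileostomy site without additional laparotomy incisions". The abdominal wall reconstruction with mesh is a separate, standardised part.
- **Analysis population (section 6.4):** "Any subject who participated in the study and underwent the study procedure". It then adds: "Patients without complete follow-up data will be excluded from the final analysis". No other population is named.
- **Aims:** section 3.2 states "The primary end point of the study is the validation of the mesh implantation procedure", without a numerical success criterion. Section 2 expects high procedural fidelity among the surgeons and "greater than 80% recruitment and retention of eligible participants, and greater than 90% adherence to the study protocol". Secondary Objective 2 lists recruitment, retention, adherence and process assessment as feasibility measures.

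The documents do not give a denominator for adherence or fidelity. They do not say how a patient converted in the operating room is counted, followed or replaced. Section 4.4.1 covers withdrawal of consent and mesh removal, but not failure to place the mesh.

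**The concern.** A feasibility pilot of a surgical technique should show how often the technique can be delivered in the patients for whom it was planned. Here a consented patient whose closure needs a laparotomy becomes ineligible after the fact and then also falls outside the all-treated set. The same can happen when a concurrent procedure is first decided during surgery. A patient in whom the retrorectus plane is developed but no mesh is placed may leave the analysis too, depending on how section 6.4 is read.

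At stake is the delivery component of adherence and of technical validation. If it is computed only where the procedure could be carried out, it says little about feasibility. The non-delivery rate, which the designers of the larger trial would want from this pilot, would not appear in the planned analysis.

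**Working it through.** **Order of events.** Recruitment is at Encounter 1 and surgery at Encounter 2. Exclusion 6 turns on whether the closure was completed through the stoma site, which is known only at or after Encounter 2. The exclusion therefore reaches patients already enrolled, and section 6.4 offers no set that would retain them.

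**Plan's own figure.** Section 6.1/6.2 takes 10% of an estimated 200-patient trial: 0.10 × 200 = 20. Section 3.1 gives the same total in two phases: 5 + 15 = 20. This reproduces.

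**Inputs.** n = 20 (section 6.1/6.2) and the adherence target of more than 90% (section 2). The non-delivery rate p is not in the documents and is assumed at 5%, 10% and 15%. Let k be the number of consented patients taken to the operating room in whom the procedure is not delivered. All other patients are taken as adherent, so that only the delivery component is examined.

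**Case A: 20 consented, no replacement.** Delivery = (20 − k)/20.

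| k | All taken to the operating room | Treated only |
|---|---|---|
| 1 | 19/20 = 95% | 19/19 = 100% |
| 2 | 18/20 = 90%, not above 90% | 18/18 = 100% |
| 3 | 17/20 = 85% | 17/17 = 100% |

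A miss needs k ≥ 2: P = 1 − (1−p)^20 − 20p(1−p)^19.
- p = 0.05: 1 − 0.3585 − 0.3774 = 0.264
- p = 0.10: 1 − 0.1216 − 0.2702 = 0.608
- p = 0.15: 1 − 0.0388 − 0.1368 = 0.824

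At an assumed 2% the same formula gives 0.06.

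**Case B: non-delivered patients replaced until 20 are treated.** Delivery = 20/(20 + k). For k = 2 this is 20/22 = 90.9%, which meets the target. For k = 3 it is 20/23 = 87.0%, which misses it. A miss means at least 3 non-deliveries among the first 22 taken to surgery: P = 1 − (1−p)^22 − 22p(1−p)^21 − 231p²(1−p)^20.
- p = 0.05: 1 − 0.3235 − 0.3746 − 0.2070 = 0.095
- p = 0.10: 1 − 0.0985 − 0.2407 − 0.2808 = 0.380
- p = 0.15: 1 − 0.0280 − 0.1087 − 0.2015 = 0.662

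In both cases the treated-only figure for delivery is 100% whatever k is. The documents do not say which case applies: section 3.1 speaks of five patients treated, and section 6.1/6.2 of 20 included.

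**The case against.** Several objections have force.

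- **Checking eligibility at surgery may be deliberate.** Exclusion 1 is also judged at takedown, and section 5.2 repeats the stoma-site condition. Restricting a technique pilot to the setting under test is defensible, and exclusion 6 also screens out planned laparotomy. This stands as a reason not to delete the item. It does not justify losing enrolled patients from the feasibility count.
- **A laparotomy for the bowel closure is not a failure of mesh implantation as such.** True: section 5.2 separates the two parts. It is still a consented patient in whom the study procedure was not delivered, and feasibility depends on that.
- **Adherence is wider than delivery.** A reader might infer that adherence reads 100% by construction. The documents do not support this. The denominator is never set, and recruitment, at least, cannot be computed in an all-treated set. Adherence to the protocol plausibly also covers technique steps, ultrasound visits and questionnaires, which implanted patients can miss. The 100% applies only to the delivery component in the treated set.
- **Abandoned implantation.** A reader might infer that these patients and their wound events disappear. They leave the analysis only if undergoing the procedure means receiving mesh, which section 6.4 does not say. Their wound events stay reportable: section 7.1 starts adverse event reporting at the initiation of any study procedure, and section 7.2 requires all adverse events in the study period to be recorded.
- **The future trial.** A reader might infer that it would face post-randomisation exclusions at the same rate. That depends on when randomisation occurs, which the documents do not state.
- **Limited consequence.** The 90% figure is an expected outcome, with no go/no-go decision attached. This stands.

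**Conclusion.** The concern holds for procedure delivery. Exclusion 6, and exclusion 5 when the need arises during surgery, act after recruitment. Together with section 6.4 they take intraoperative conversions out of the analysis, and they may take out abandoned implantations. The delivery component of adherence and technical validation then rests on patients in whom the procedure could be carried out.

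The size cannot be fixed, because no conversion rate is given and replacement is not addressed. Over assumed rates of 5% to 15%, the chance that non-delivery alone would bring the rate to 90% or below is 26% to 82% without replacement and about 9% to 66% with it. These figures assume independent patients and full adherence otherwise. The structural point needs none of them. It should be corrected before the feasibility results are analysed, and the correction is cheap.

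**What to change.** 1. **Section 4.2:** keep planned laparotomy and planned concurrent procedures as enrolment exclusions. In a consented patient, reclassify conversion, an unplanned concurrent procedure or abandoned implantation as a recorded outcome, *study procedure not delivered*, with the reason.
2. **Section 6.4:** add an attempted set, defined as all consented patients taken to the operating room, as the denominator for procedure delivery and adherence. State whether non-delivered patients are replaced and whether they count toward the first five patients in section 3.1.
3. **Wound occurrences:** keep the implanted set for 30-day mesh wound occurrences and the historical comparison. Tabulate separately any wound occurrences after retrorectus dissection without mesh. These are already captured as adverse events.

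**Cost:** wording in two sections and one CRF field, with no extra patients or procedures. The reported delivery and adherence rates may be slightly less favourable.
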